7 STUDY DESIGN

7.1 Overall Design

This is a Phase 2B randomized, double-blind, placebo-controlled, dose ranging, 6-arm, parallel-design study. Subjects will receive a primary unilateral first metatarsal bunionectomy repair on Day -1 (Figure 7-1). A continuous popliteal sciatic block infusion (0.2% ropivacaine) will be started after surgery and will be removed between 3AM and 5AM on Day 1. After removal of the popliteal sciatic block, a subject can be randomized once the subject requests the first dose of study drug for pain relief, and the subject's pain is ≥4 on the NPRS and is moderate or severe on the VRS (Verbal Categorical Rating Scale). If a subject does not meet the NPRS and VRS criteria within 9 hours of removal of the popliteal sciatic block, the subject will not be eligible to enroll in the study.

A total of approximately 242 subjects will be randomized 2:2:2:2:1:2 to 6 treatment arms, evaluating a range of 5 VX-150 dose levels as shown in Table 7-1.

Table 7-1 VX-150 Doses by Treatment Arm

Treatment	Dose Level	Dose	Number of Subjects
VX-150	1 (highest)	First dose 1500 mg, then 750 mg q12h	44
	2	1000 mg qd	44
	3	500 mg q12h	44
	4	First dose 500 mg, then 250 mg q12h	44
	5 (lowest)	250 mg qd	22
Placebo			44

[figure not shown]
q12h: every 12 hours; qd: daily

Note: q12h dosing will be through 36 hours after the first dose of study drug throughout the protocol.

Subjects will report their pain on the NPRS at scheduled time points (See Table 3-2 in CSP) through 48 hours after the first dose of study drug. In addition, pain intensity will be recorded

on the NPRS immediately before each administration of rescue medication. Subjects are encouraged to wait 90 minutes after the first dose of study drug to receive rescue medication, and subjects should generally not receive rescue medication unless their NPRS is ≥4. However, subjects may receive rescue medication at any time after the first dose of study drug per their request. The rescue medication will be ibuprofen (400 mg [oral] every 4 hours [q4h] as needed [prn]).

Figure 7-1 VX18-150-104 Study Design

CRU: clinical research unit; NPRS: Numeric Pain Rating Scale; VRS: Verbal Categorical Rating Scale Notes: After removal of the popliteal sciatic block, a subject can be randomized once the subject requests the first dose of study drug for pain relief, and the subject's pain is ≥4 on the NPRS and is moderate or severe on the VRS. VX-150 dose levels (Dose Levels 1 [highest], 2, 3, 4, and 5 [lowest]) are shown in Table 7-1. To maintain the blind, all subjects will receive the same number of capsules.

7.2 Sample Size and Power

The sample size calculation is based on the primary analysis of the primary efficacy endpoint. The primary efficacy endpoint is the time-weighted sum of the pain intensity difference 0 to 24 hours after the first dose (SPID24). The primary analysis of this endpoint is to detect if there is a significant dose-response relationship across VX-150 dose groups and placebo using the MCP-Mod (multiple comparison procedures with modeling techniques). Under MCP-Mod, a pre-specified candidate set of 4 dose-response models (Linear, Emax, Logistic, and Sigmoid Emax) is proposed.

Assuming the maximum effect size compared to placebo is 0.7, 40 evaluable subjects in the placebo, VX-150 Dose Level 1 (highest), 2, 3, and 4 groups, and 20 evaluable subjects in VX-150 Dose Level 5 (lowest) group would provide approximately at least 88% power to detect a dose-response relationship from the candidate set with a 5% level of significance. In addition, 40 evaluable subjects per treatment group can provide at least 85% power to detect an effect size of 0.7 compared to placebo. In order to allow for withdrawal of up to 10% of randomized subjects, the study will enroll and randomize approximately 242 subjects in total.

7.3 Randomization

A total of approximately 242 subjects will be randomized 2:2:2:2:1:2 to 6 treatment arms. Randomization will be stratified by site and sex. To maintain the blind, all subjects will receive the same number of capsules in a double-dummy design.

An interactive web response system (IWRS) will be used to assign subjects to treatment. The randomization code will be produced by Vertex Biostatistics or a qualified randomization vendor. The Vertex study biostatistician will review and approve the production of the final randomization list, which will be reviewed and approved by a designated unblinded biostatistician who is not a member of the study execution team (SET).

7.4 Blinding and Unblinding

Refer to Section 10.7 of the CSP for details.

8 ANALYSIS SETS

8.1 All Subjects Set

The **All Subjects Set** will be defined as all subjects who have been randomized or have received at least 1 dose of study drug. This analysis set will be used in subject listings and disposition summary table, unless otherwise specified.

8.2 Full Analysis Set

The **Full Analysis Set (FAS)** will be defined as all randomized subjects who have received at least 1 dose of study drug. The FAS will be used to summarize subject demographics, baseline characteristics, and for all efficacy analyses in which subjects will be analyzed according to their randomized treatment group.

8.3 Safety Set

The **Safety Set** is defined as all subjects who have received at least 1 dose of study drug. The Safety Set will be used for all safety analyses in which subjects will be analyzed according to the treatment they received.

9 STATISTICAL ANALYSIS

9.1 General Considerations

The Schedule of Assessments is provided in Section 3 of CSP. The precision standards for reporting safety and efficacy variables are provided in an internal Biometrics document that specifies the programming rules including the precision for derived variables.

Continuous variables will be summarized using the following descriptive summary statistics: the number of subjects (n), mean, standard deviation (SD), median, minimum value (min), and maximum value (max), unless otherwise specified.

Categorical variables will be summarized using counts and percentages.

Baseline value for NPRS will be defined as the most recent non-missing measurement collected on Day 1 before the first dose of study drug. For all other variables, unless

Protocol Number: VX18-150-104

otherwise specified, baseline value will be defined as the most recent non-missing measurement (scheduled or unscheduled) collected before the first dose of study drug.

Change (absolute change) from baseline will be calculated as post-baseline value – baseline value unless otherwise specified.

Treatment-emergent (TE) Period will be defined as the time from first dose of study drug through the Safety Follow-up (for enrolled subjects who do not have a Safety Follow-up Phone Interview: it will be defined as the time from first dose of study drug through 9 days after the last dose of study drug)

Unscheduled visits: Unscheduled visit measurements will be included in analysis as follows:

- In scheduled visit windows per specified visit windowing rules.
- In the derivation of baseline/last on-treatment measurements.
- In the derivation of maximum and minimum values during TE period, and maximum and minimum change from baseline values during TE period for safety analyses
- In individual subject data listings as appropriate.

Visit windowing rules: The analysis visit windows for protocol-defined visits are provided in Appendix A.

Incomplete/missing data will be imputed for NPRS by applying linear interpolation to the valid observations immediately before and after the missing observation(s). If there are no valid observations after the missing observation(s) the last observation carried forward (LOCF) principle will be applied as a primary approach. Additional details on how to handle missing data is described in subsequent sections when applicable.

Outliers: No formal statistical analyses will be performed to detect or remedy the presence of statistical outliers, unless otherwise specified.

Multiplicity: No multiplicity adjustment will be performed for hypothesis testing except for MCP-Mod procedure in Section 9.3.1.2 and 9.3.1.3.

9.2 Background Characteristics

9.2.1 Subject Disposition

The number of subjects in the following categories will be summarized overall and by treatment group:

- All Subjects Set
- Randomized
- Full Analysis Set (FAS)
- Safety Set

The number and percentage (based on FAS) of subjects in each of the following disposition categories will be summarized overall and by treatment group:

- Completed study drug treatment
- Prematurely discontinued the study drug treatment and the reason for discontinuation
- Completed study (i.e., completed Safety Follow-up Phone Interview)
- Prematurely discontinued the study and the reason for discontinuation

A listing will be provided for subjects who discontinued study drug treatment or who discontinued study with reasons for discontinuation. A randomization listing of subjects will be provided.

9.2.2 Demographics and Baseline Characteristics

Demographics and baseline characteristics will be summarized overall and by treatment group based on the FAS.

Demographic data will include the following:

- Age (in years)
- Sex (male, female)
- Ethnicity (Hispanic or Latino, not Hispanic or Latino, and not collected per local regulations)
- Race (White, Black or African American, Asian, American Indian or Alaska Native, Native Hawaiian or Other Pacific Islander, not collected per local regulations, Other and Multiracial [if more than 2 races reported from a subject])

Baseline characteristics will include the following:

- Weight (kg)
- Height (cm)
- BMI (kg/m²)

Disease characteristics will include the following:

- Pain intensity at baseline as recorded on the NPRS
- VRS at baseline

In addition, data listings will also be provided for:

- Inclusion/Exclusion criteria violation for subjects with any such violations
- Supplemental analgesic medications administered after surgery and before removal of the popliteal sciatic block

9.2.3 Medical History

Medical history will be coded by using the Medical Dictionary for Regulatory Activities (MedDRA). For the FAS, medical history will be summarized descriptively by system organ class (SOC) and preferred term (PT). The corresponding data listing will also be provided.

9.2.4 Prior and Concomitant Medications

Medications taken 14 days before the Screening Visit and up to the Safety Follow-up will be coded and summarized by Preferred Name using the World Health Organization-Drug Dictionary (WHO-DD) for the FAS as frequency tables in 2 parts:

- 1. Prior medication: Medication that started before the first dose of study drug, regardless of when dosing of the medication ended.
- 2. Concomitant medication: Medication received at or after the first dose of study drug, medication that was received before initial dosing and continued after initial dosing of study drug, or medication with missing stop date.

Medication that started before the first dose of study drug and continued after the first dose of study drug will be summarized as prior medication and separately as concomitant medication.

If a medication has completely missing or partially missing start/stop dates and it cannot be determined whether it was taken before the first dose or concomitantly, it will be classified as prior and concomitant.

Details for imputing missing or partial start/stop date and time of medication are described in Appendix B.

9.2.5 Study Drug Exposure and Study Drug Compliance

Study drug will be administered to the subjects by site personnel at time points specified in Table 3-2 and as described in Section 9.6 of CSP during a period of 36 hours. Therefore, it is not needed to perform a calculation of exposure to study drug or a calculation of compliance. All data collected during dispensation of study drug, i.e. time of administration and number of capsules taken, will be presented in an individual data listing only.

9.2.6 Important Protocol Deviations

Important protocol deviation (IPD) is a subset of protocol deviations (any change, divergence, or departure from the study design or procedures defined in the protocol) that may significantly impact the completeness, accuracy, and/or reliability of the study data or that may significantly affect a subjects' rights, safety or well-being. IPDs will be identified from the clinical database and/or site deviation log.

A list of categories of IPDs identified for this study is presented in Appendix E.

All IPDs will be summarized descriptively by treatment group and presented in an individual subject data listing.

9.3 Efficacy Analysis

Unless otherwise defined, all efficacy analyses described in this section will be based on the FAS. Subjects will be analyzed according to their randomized treatment assignment.

9.3.1 Analysis of Primary Efficacy Variable

9.3.1.1 Definition of Primary Efficacy Variable

The primary efficacy endpoint is the time-weighted sum of the pain intensity difference 0 to 24 hours (SPID24) after the first dose of VX-150 or placebo.

In general SPID is calculated as: $\sum \Delta time_i \times PID_i$

Where:

- $\Delta time_i = time$ (in hours) elapsed since previous measurements
- PID_i = pain intensity at baseline when the subject requests the first dose of study medication pain intensity at hour i

Hence:

• SPID24 = $0.5 \times \text{PID}_{0.5} + 0.5 \times \text{PID}_1 + 0.5 \times \text{PID}_{1.5} + 0.5 \times \text{PID}_2 + \text{PID}_3 + \text{PID}_4 + \text{PID}_5 + 2 \times \text{PID}_8 + 4 \times \text{PID}_{12} + 4 \times \text{PID}_{16} + 4 \times \text{PID}_{20} + 4 \times \text{PID}_{24}$

As stated in Section 9.1, intermittent missing data will be imputed for NPRS by applying linear interpolation to the valid observations immediately before and after the missing observation(s) during 0 to 48 hours. Such intermittent missing data are assumed to be missing completely at random.

Pain intensity scores that were collected within 4 hours after a dose of rescue medication (rescue period) will not be used in the analysis. Instead, these observations will be imputed with the pain assessment completed immediately before the administration of rescue medication. If that pain assessment is missing, the last non-missing regular pain intensity score will be applied (the LOCF principle). This approach assumes that the effect of the study drug on pain intensity score remains the same as the pre-rescue measurement during the first 4 hours after administration of rescue medication.

If there are multiple administrations of rescue medication within the same 4 hour period, a local highest pain intensity score will be used for the imputation during the second 4 hours rescue period. The local highest pain intensity score is the highest values among the first pre-rescue, the second pre-rescue and the actual observed (if any) in the overlapping period.

If a subject discontinues the study drug treatment prior to 24 hours, the LOCF principle will be used to impute all pain intensity scores up to 24 hours, irrespective of reason for study drug treatment discontinuation so that SPID24 can be calculated accordingly. Even if a subject completes the study, but has missing data from a certain time point to hour 24, the LOCF principle will be used to impute all pain intensity scores up to 24 hours. The last observed pain intensity score should be from a regularly scheduled measurement including a previous pre-rescue assessment, but cannot be any actual measurements taken during a previous rescue period. The LOCF principle assumes that the last observed pain intensity score represents the effects of study drug in the remaining of study period towards the

planned endpoint, regardless of reason for discontinuation and if the subject completes the study or not.

The imputation order will be: (1) intermittent missing data (2) 4 hours after administration of rescue medication and (3) missing data from a certain time point towards the planned endpoint including after early discontinuation from study drug treatment.

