Medications review	Continuous from signing of ICF through Safety Follow-up Continuous from signing of ICF through Safety Follow-up				
Treatments and procedures review					

β-hCG: beta-human chorionic gonadotropin; CRU: clinical research unit; NPRS: Numeric Pain Rating Scale; PK: pharmacokinetic; VRS: Verbal Categorical Rating Scale

Starting on Day 1, subjects will report their pain on the NPRS at 0.5, 1, 1.5, 2, 3, 4, 5, 6, 8, 12, 16, 20, 24, 28, 32, 36, 40, 44, and 48 hours (± 5 minutes) after the first dose of study drug. In addition, pain intensity on the NPRS will be recorded when the subject requests the first dose of study drug for pain relief and immediately before each administration of rescue medication.

Continuous from signing of ICF through Safety Follow-up

on Day 1, subjects will report their pain on the VRS when they request the first dose of study drug for pain relief.

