9.3.2 Study Drug Dose and Duration

Five dose levels of VX-150 (Dose Levels 1 [highest], 2, 3, 4, and 5 [lowest]) will be evaluated as shown in Table 9-1. The highest dose level (Dose Level 1 [first dose 1500 mg, then 750 mg every 12 hours (q12h)]) will not exceed a maximum dose of 2250 mg per day. The maximum dose has been selected on the basis of favorable safety and VRT-1207355 PK results after oral dosing with VX-150 in

VX16-150-103 (Study $\overline{103}$). Multiple oral doses up to 1750 mg qd VX-150 for 14 days have been evaluated and found to be safe and well tolerated. Additionally, the treatment duration is the same as in Study 103.

The highest dose level (Dose Level 1) to be tested (2250 mg per day; first dose 1500 mg followed by doses of 750 mg q12h) was evaluated in Study 103 in subjects with acute pain following bunionectomy. After administration of the first dose of VX-150 on Day 1 and Day 2, the mean VRT-1207355 maximum observed concentration (C_{max}) of 4.95 µg/mL (Day 1) and 4.92 µg/mL (Day 2) exceeded the concentration resulting in 50% of the maximum inhibition (IC_{50}) for inhibition of Na_v1.8. The maximum concentrations for VRT-1207355 were reached approximately 5.58 hours after the first dose on Day 1 and 4.03 hours after the first dose on Day 2. A statistically significant treatment effect was observed at 24 hours following the first and second doses, favoring VX-150 compared to placebo. VX-150 was generally well tolerated in these subjects without any significant safety concerns.

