9.3.2 Analysis of Secondary Efficacy Variables

9.3.2.1 Definition of Secondary Efficacy Variables

Time-weighted sum of the pain intensity difference between VX-150 versus placebo as recorded on a NPRS 0 to 48 hours (SPID48) after the first dose: SPID48 will be calculated using the following formula:

 $\begin{array}{l} \bullet \quad SPID48 = 0.5 \times PID_{0.5} + 0.5 \times PID_1 + 0.5 \times PID_{1.5} + 0.5 \times PID_2 + PID_3 + PID_4 + PID_5 \\ + PID_6 + 2 \times PID_8 + 4 \times PID_{12} + 4 \times PID_{16} + 4 \times PID_{20} + 4 \times PID_{24} + 4 \times PID_{28} + 4 \times PID_{32} + 4 \times PID_{36} + 4 \times PID_{40} + 4 \times PID_{44} + 4 \times PID_{48} \end{array}$

Proportions of subjects with at least 30%, 50%, or 70% reduction in NPRS at 24 hours after the first dose of VX-150 versus placebo: A subject with at least 30%, 50%, or 70% reduction in NPRS at 24 hours after the first dose of study drug will be defined as a "responder". The percentage reduction in the NPRS will be calculated as following:

• 100 × (NPRS at baseline –NPRS at 24 hours) / NPRS at baseline

If a subject discontinues the study drug treatment for any reason prior to 24 hours, this subject will not be a "responder" for any of the three criteria. If a subject has missing NPRS at 24 hours without discontinuing the study drug treatment prior to 24 hours, the LOCF principle will be used to impute pain intensity score at 24 hours. The last observed pain intensity score should be from a regularly scheduled measurement including a previous prerescue assessment, but cannot be any actual measurements taken during a previous rescue period.

Time to onset of "confirmed perceptible pain relief" and "meaningful pain relief" after the first dose of VX-150 versus placebo: Time to onset of "perceptible pain relief" is the time elapsed from first dose of VX-150 or placebo until the subject stops the "perceptible pain relief" stopwatch. Time to onset of "meaningful pain relief" is the time elapsed from first dose of VX-150 or placebo until the subject stops the "meaningful pain relief" stopwatch. Time to onset of "confirmed perceptible pain relief" will be defined as the time to onset of perceptible pain relief for those subjects who had meaningful pain relief.

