12 LIST OF APPENDICES

Appendix A: Analysis Visit Windows for Safety and Efficacy Assessments

Assessment	Visit/Time Point ¹	Target Study Day /Time Point per the protocol	Analysis Visit Window (in study days/ time points)
Safety Assessment			
Hematology Serum Chemistry Coagulation	Baseline	-1	[Screening visit, Pre-dose Day 1]
Standard 12-Lead ECG	Baseline	1	[Screening visit, Pre-dose Day 1]
	Day 1, 4 hours	4 hours after the first dose of study drug	3 – 5 hours after the first dose of study drug on Day 1
Vital Sign	Baseline	1	[Screening visit, Day 1]
	Day 2	2	2
	Day 3	3	3
Efficacy Assessment			
NPRS	Baseline	1	[After removal of the popliteal sciatic block, Pre-dose Day 1]
	At 0.5, 1, 1.5, 2, 3, 4, 5, 6, 8, 12, 16, 20, 24, 28, 32, 36, 40, 44, and 48 hours	1 - 3	± 5 minutes for 0.5 to 12 hours ± 10 minutes for 16 to 48 hour
VRS	Baseline	1	[After removal of the popliteal sciatic block, Pre-dose Day 1]

Notes:

The analysis visit windows will be applied using the following rules for both scheduled and unscheduled visits:

- 1. If no numerical measurement is available within a visit window, the measurement will be considered missing for the visit.
- 2. If there is more than 1 numerical measurement available within the same visit window, use the following rules:
 - a. a. For efficacy assessments: if there are multiple measurements within a visit window,
 - i. The measurement closest to the target day/time point will be used; or
 - ii. If there are multiple measurements within the same distance from the target day/time point, the latest measurement will be used.
 - b. For **safety** assessments: if there are multiple measurements within a visit window,
 - i. The measurement closest to the target day/time point will be used; or

¹Visit/Time point name for analysis purpose is used to report data in tables and figures.

Protocol Number: VX18-150-104

- ii. If there are multiple measurements within the same distance from the target day/time point, the latest measurement will be used.
- 3. When define efficacy and safety at baseline, refer to the generic baseline definition in Section 9.1. If hour and/or minute of first dose time are missing, baseline will be defined as the most recent non-missing measurement collected before the date of first dose of study drug.
- 4. For vital sign, if scheduled and unscheduled measurements at the same date, the scheduled measurement will be used.
- 5. Age (in years) at first dose date (for demographics, listing):

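### The SAP's written-out SPID24 formula drops the 6-hour score, so its weights add up to 23 hours instead of 24

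*SAP*

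**What the plan says.** SAP 9.3.1.1 describes the primary variable as the "time-weighted sum of the pain intensity difference 0 to 24 hours (SPID24) after the first dose of VX-150 or placebo". It gives a general rule: multiply each PID by the hours since the preceding measurement, then add. It then writes the SPID24 sum out as a consequence of that rule. Around hour 6 the written-out sum reads "PID}_5 + 2 \times \text{PID}_8 + 4 \times \text{PID}_{12", with no 6-hour term between hours 5 and 8.

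Three other places bear on this:

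- SAP 9.3.2.1, in the SPID48 formula, has the 6-hour term: "PID_6 + 2 \times PID_8 + 4 \times PID_{12".
- Protocol Section 3 (NPRS footnote to Table 3-2) schedules scores at "0.5, 1, 1.5, 2, 3, 4, 5, 6, 8, 12, 16, 20, 24, 28, 32, 36, 40, 44, and 48 hours".
- SAP Appendix A lists the same NPRS analysis time points: "At 0.5, 1, 1.5, 2, 3, 4, 5, 6, 8, 12, 16, 20, 24, 28, 32, 36, 40, 44, and 48 hours".

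Protocol 12.3.3.1 names SPID24 but gives no formula, so the SAP line is the only explicit one. Under SAP 9.3.1.2, SPID24 is the dependent variable of the ANCOVA on which MCP-Mod, the LS means and the fitted dose-response curve are based.

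**The concern.** The written-out formula does not follow from the rule stated just above it. A programmer working from the rule and the schedule obtains a 24-hour sum. One who copies the printed line obtains a 23-hour sum. Both could claim to have followed the SAP, and their values would differ in every subject whose 6-hour PID is not zero.

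If the printed line is used, every SPID24 mean and treatment difference is on a different scale from the one the endpoint's name implies, and SPID24 is no longer the first-24-hour part of SPID48. The dropped score is also the scheduled one nearest the peak drug level reported for the highest regimen in the previous bunionectomy study (Protocol 9.3.2): "The maximum concentrations for VRT-1207355 were reached approximately 5.58 hours after the first dose on Day 1". If the slip came to light after database lock, correcting it would be a late change to the primary variable, which the SAP Introduction says must be documented in the study report.

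**Working it through.** **1. Sum of the weights**

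The inputs are the printed formulas (SAP 9.3.1.1 and 9.3.2.1) and the NPRS schedule (Protocol Table 3-2, SAP Appendix A).

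| Version | Hours 0.5–2 | Hours 3–6 | Hour 8 | Hour 12 onward | Total |
|---|---|---|---|---|---|
| SPID24 as printed | 4 × 0.5 = 2 | 3 × 1 = 3 (hours 3, 4, 5) | 2 | 4 × 4 = 16 | **23** |
| SAP rule applied to the schedule | 2 | 4 × 1 = 4 (hours 3, 4, 5, 6) | 2 | 16 | **24** |
| SPID48 as printed | 2 | 4 | 2 | 10 × 4 = 40 | **48**, of which 24 through hour 24 |

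**2. Could hour 6 have been left out on purpose?**

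The measurement before hour 8 would then be hour 5, and the rule would give hour 8 a weight of 8 − 5 = 3, for a total of 2 + 3 + 3 + 16 = 24. The printed weight is 2 = 8 − 6, which is right only if a 6-hour score precedes it. The line breaks the rule on either reading.

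**3. Size for the estimate**

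Per subject, intended SPID24 − printed SPID24 = 1 × PID_6. With a constant PID the loss is 1/24 = 4.2%. In an illustrative simulation (assumed baseline about 7, effect about 1.4 NPRS points, SPID24 SD about 40), the treatment difference fell from 31.25 to 29.91 pain-hours: 1.34/31.25 = 4.3%. The standardised effect went from 0.762 to 0.759.

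**4. Size for power**

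First, the plan's own figure. SAP 7.2 claims at least 85% power with 40 per group and effect size 0.7. The normal approximation at two-sided 5% gives Φ(0.7 × √(40/2) − 1.96) = Φ(1.17) = 0.879, and the t-test with 78 df gives 0.871. The claim is reproduced.

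Next, the intended 24-hour sum was scaled to an effect size of 0.70, and the effect size of the 23-hour sum was computed under assumed within-subject correlations (compound symmetry 0.3 to 0.8; autoregressive 0.9 and 0.95 per hour). The two sums correlate at 0.998 or more throughout.

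| Assumed treatment effect over time | Treatment difference kept | Effect size, printed formula | Pairwise power |
|---|---|---|---|
| Flat | 95.8% | 0.694–0.699 | 0.874–0.878 |
| Broad peak at 5.58 h: exp(−((t − 5.58)/4)²) + 0.3 | 90.1% | 0.653–0.657 | 0.831–0.836 |
| Narrow peak at 5.58 h: exp(−((t − 5.58)/1.5)²) + 0.2 | 84.2% | 0.610–0.614 | 0.779–0.785 |

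The documents give no treatment effect by time point, so all three profiles are assumptions. The peaked ones show how far the loss could reach; they are not predictions.

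**5. Distance from the stated peak**

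|6 − 5.58| = 0.42 h and |5 − 5.58| = 0.58 h. The omitted score is the nearest, by 0.16 h.

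**The case against.** The strongest reply is that the intended formula is not in doubt. The rule, the schedule, the endpoint's name, the weight of 2 on hour 8 and the SPID48 formula all require the 6-hour term, so the SAP defines a 24-hour endpoint and one line contradicts it. The term may even have been lost in reading the PDF: the extracted text also lacks the minus sign in the definition of PID, and the SPID48 formula breaks across lines just before its 6-hour term. This stands as a reason to look at the typeset page. It does not clear the line, which reads as complete, and the harm has always depended on someone coding it literally.

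A second reply is that the consequence is small. The same weights apply in every arm, so the omission does not in itself favour any arm and the test remains valid. With a flat effect, power moves by half a percentage point or less. That is correct, and it means the case rests on the reported estimates and on having a single definition of the primary variable.

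A third reply concerns peak concentration. The 5.58 h figure comes from one study at the highest regimen, no peak times are given for the other four dose levels, and the documents do not show that peak concentration is peak analgesia. The 5-hour score, almost as close, stays in. For subjects who took rescue in the preceding 4 hours, the 6-hour score would in any case be replaced by the pre-rescue one. All of this stands. The peak is supporting context only, and the error is there without it.

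**Conclusion.** The concern holds. As printed, the SPID24 formula covers 23 of 24 hours and contradicts the SAP's own rule, its schedule and its SPID48 formula. It is very probably a dropped term and not a design choice.

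If it is programmed literally, each subject's SPID24 is off by exactly the 6-hour PID, about 4% of the total when PID is roughly constant. The standardised effect and power are then almost unchanged. A material loss of power (to about 0.78–0.84 from 0.88) appears only under assumed profiles that concentrate the effect near 5.58 h. The sample-size statement is not affected, because it rests on a standardised effect size and not on this formula.

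The conclusion assumes that the typeset page matches the text quoted here. The size of the harm in practice depends on whether the derivation program follows the printed line, which the documents do not show.

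**What to change.** Check the formula against the typeset SAP page. If the term is absent there, insert + PID_6 between PID_5 and 2 × PID_8 in SAP 9.3.1.1. The weights then sum to 24 and match the SPID48 formula term by term through hour 24. Confirm that the SPID24 derivation program, and any independent check of it, uses the 6-hour score with weight 1. Do this before database lock.

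The cost is one term in the SAP and a check of the program. The 6-hour score is already scheduled, so no new data, visits or subjects are needed.
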